18.03.2021

**EVALUATION OF PRESSURE INJURY PREVENTION
CARE BUNDLE APPLICATION IN INTENSIVE CARE
UNIT PATIENTS DIAGNOSED WITH INTERNAL
DISEASES**

**STUDY PROTOCOL AND STATISTICAL
ANALYSIS PLAN**

NCT ID: Not yet assigned

STUDY PROTOCOL AND STATISTICAL ANALYSIS PLAN

Objective and Setting

The present study is a quasi-experimental study with a control group conducted in order to evaluate the application of pressure injury prevention care bundle in intensive care unit patients diagnosed with internal diseases.

Hypothesis

H0: The application of the pressure injury prevention care bundle is not effective in preventing pressure injury development.

H1: The application of the pressure injury prevention care bundle is active in preventing pressure injury development

Study Universe and Sample

The universe of the study consisted of patients hospitalized in the intensive care unit patients diagnosed with internal diseases in training and research hospital. The study sample was made up of diagnosed with internal diseases patients who were hospitalized in the intensive care unit between July-December 2021, who met the inclusion criteria, and who agreed to participate in the study. Power analysis was performed in order to determine the number of patients to be included in the study. The power of the test was calculated through G*Power 3.1 software. In order to determine the development status of pressure injuries in the intervention and control groups, 98 patients were included in the study with a minimum number of 49 patients in each group.

Inclusion and Exclusion Criteria

Patients who were 18 years old and above, who did not have any pressure injuries on any part of their body, who were expected to stay in the clinic for at least 24 hours, and who were diagnosed with an internal disease were included in the study. The patients who were younger than 18 years, who had a pressure injury on any part of their body, who were expected to stay in the clinic for less than 24 hours, and who had intensive care indications other than an internal disease were excluded from the study.

The end criteria for the study was determined as follows;

- Death of the patient, reaching the desired number of patients, discharging the patient from the clinic, the development of pressure injury in the patient.

Data Collection Instruments

A. Patient Information Form: The form prepared by the researcher includes questions inquiring about the sociodemographic and background information of the patients (age, gender, body weight, height, smoking and alcohol use), clinical characteristics (date of hospitalization, hospitalization diagnosis, duration of stay in intensive care unit, Braden risk assessment tool score, being provided with mechanical ventilation or not, medicines used, development and staging of pressure injury), and laboratory results (hemoglobin, hematocrit, blood glucose level, saturation, prealbumin value).

B. Pressure Injury Prevention Care Bundle Form: The form was developed by the researcher by benefiting from the Prevention and Treatment of Pressure Injury – 2019 Quick Reference Guide, European Pressure Injury Advisory Panel (EPIAP), and National Pressure Injury Advisory Panel (NPIAP) (2016) guidelines (**Figure 2**). The pressure injury prevention care bundle includes risk assessment (risk is assessed using braden risk scale, the assessment is carried out within the first 8 hours, then it's done every day, if there is a change in the status of the individual, it will be re-evaluated), skin assessment (the skin is evaluated for non-fading redness by printing, localized temperature, edema and humidity, it is evaluated in each shift or change of state, pressure zones in contact with the medical device are evaluated every 12 hours), skin care (the skin is clean and kept in normal humidity, the areas of the fritz are not rubbed vigorously, they are not massaged, every 8 hours the barrier feature protects the product and skin, the skin is protected from urine and fecal incontinence, sheets are kept clean, tense and dry), positioning (every two hours, the right-hand side-back-left-side position is given 30°, respectively, the pressure on the bone protrusions is reduced, the heels are prevented from touching the bed and are maintained), regulation of nutrition and liquid management (individual enteral or parenteral nutrition is provided, the patient's fluid intake is evaluated, dehydration is evaluated, weekly albumin/crp values are monitored) ^{1,6,9,10}

In intervention of applying each parameter in the bundle, “yes” is marked, and “no” is marked when each parameter is not applied, when each recommendation is applied, it is considered full compliance with the bundle.¹¹⁻¹² After the bundle has been prepared, 4 intensive care nurses, 2 academics who are qualified in intensive care and internal diseases nurses, and 7 specialist docs were presented to the opinion of the Medical Specialty Education Institution (TUEK), where the study was conducted.

C. Braden Risk Assessment Tool: The tool was developed by Braden and Bergstrom in 1987 by considering risk factors involved in pressure injuries. With this tool, six parameters of the patient’s stimulant perception, activity, mobility, the effect caused on the skin by humidity, friction, and shearing tension are measured. 12 points and below in total are considered high risky, 13-14 points risky, 15-16 points low risky, and for individuals at the age of 75 and above, 15-18 points are evaluated to be low risky. In addition, it is recommended to be used in intensive care units and patients who need long-term care. This tool is routinely used in the clinic where the study was conducted.¹³⁻¹⁵

Data Collection

The study was conducted in three stages. The stages of the study are presented in **Figure 1**.

Stage 1: In the first phase of the study, the pressure injury prevention care bundle, consisting of 5 substances related to risk assessment, skin assesment, skin care, positioning, regulation of nutrion and liquid management, has been developed. After the bundle has been created, a training presentation has been prepared for nurses working in the clinic, including general information on pressure injury within the literature, the pressure injury prevention care bundle and information on how to use the bundle.

Once all of these preparations have been completed, the control group has been included in the study by continuing routine practices for pressure injury in the clinic (using of braden risk scale, positioning, elevation of the heels). After completing the patient acquisition of the control group, an appropriate training schedule has been created to perform the previously prepared training program, taking into account the nurses' work schedule in the clinic. The training program has been carried out to 40 nurses working in ICU between 30-45 minutes in 4 separate meetings. After the training, training presentations were given to the nurses.

Stage 2: After the training, the pressure injury prevention care bundle was applied to the patients in the intervention group who met the inclusion criteria until the determined number of patients was reached.

Stage 3: At this stage, it was examined whether any pressure injuries developed in the patients in the group who were applied the pressure injury care bundle, and the effectiveness of the pressure injury care bundle was evaluated.

Data Evaluation and Statistical Methods

The study data were analyzed through IBM SPSS V23 software. In the categorical comparison of the groups, Yates Correction, Fisher's Exact test, and Pearson χ^2 test were employed. In the two-group comparison of the normally distributed data, Independent Two Samples t test was used, while in the comparison of the data without normal distribution, Mann-Whitney U test was used.

The risk factors affecting the process of disease development were analyzed with Cox regression analysis. In the comparison of survival duration according to VOD status, Log Rank test was employed. The analysis results were presented as mean \pm standard deviation for the quantitative data and as frequency (percentage) for the categorical variables. Significance level was taken as $p<.05$.

Ethics

In conducting study, universal ethical rules as well as scientific principles were observed. As the use of human beings in the study required the protection of individual rights, the principles of Helsinki Declaration of Human Rights were also observed. Ethics board approval was obtained from the Health Sciences University Hamidiye Interventional Research Ethics Committee (**Decision No: 2021.03.18-33**) and institutional permission was taken from the hospital where the study would be conducted and Medical Specialty Education Authority. Moreover, before collecting the study data, each patient participating in the study or their legal custodian was informed about the content of the study and nurses, voluntary participation, and their verbal and written consents were taken.

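### With no fixed observation period and groups from different periods, a crude comparison of injury percentages cannot separate fewer injuries from faster ICU exit, and no time-to-injury comparison of bundle and control is planned

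*Combined protocol and SAP*

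**What the plan says.** The end criteria, in the Inclusion and Exclusion Criteria section, are: "Death of the patient, reaching the desired number of patients, discharging the patient from the clinic, the development of pressure injury in the patient". Patients need an expected stay of at least 24 hours. There is no upper limit and no fixed day at which injury status is read.

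Under Data Evaluation and Statistical Methods, three sentences bear on the outcome:

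- On categorical data: "In the categorical comparison of the groups, Yates Correction, Fisher's Exact test, and Pearson χ^2 test were employed". Results are shown "as frequency (percentage) for the categorical variables".
- On the log-rank test: "In the comparison of survival duration according to VOD status, Log Rank test was employed". VOD is not defined anywhere.
- On the Cox model: "The risk factors affecting the process of disease development were analyzed with Cox regression analysis". This sentence gives no event, time origin, group term or censoring rule.

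No sentence says how death, discharge or a patient still in the unit at the cut-off is to be coded.

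Under Data Collection, control enrolment was completed before the nurses were trained, and bundle patients were enrolled after the training. The Patient Information Form lists hospitalization date, length of ICU stay, and injury development and stage. It lists neither the date of injury nor the way the patient left the unit.

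**The concern.** H1 asks whether the bundle prevents pressure injury. A patient who dies or is discharged can no longer have an injury observed in the unit, so the share injured depends on two things: how fast injuries occur, and how long patients stay at risk. The bundle is meant to change the first. The second can change between two calendar periods through case mix, bed pressure or mortality, with no contribution from the bundle.

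A two-by-two table of injured against not injured merges the two. If bundle-period patients leave sooner, the table can show prevention where the injury hazard is unchanged. If they stay longer, it can hide a real reduction.

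A second gap lies in the end criteria. If reaching the target number stops observation of patients still in the unit, their follow-up is incomplete, and a crude table counts them as uninjured.

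**Working it through.** **The plan's own figure.** The Study Universe and Sample section says "98 patients were included in the study with a minimum number of 49 patients in each group" and names the software, but gives no injury rates, effect size, power or sidedness. The 98 can therefore be neither confirmed nor refuted. At two-sided 5% and 80% power without continuity correction, 49 per group fits 30% v 8%, 40% v 15% or 50% v 23%, among others. Nothing below depends on it except the group size of 49.

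**Inputs.** The documents give no injury, death or discharge rates. All hazards below are assumptions, constant over time. Let *l* be the daily injury hazard and *c* the daily hazard of death and discharge combined.

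**Formulas.**
- Share injured by ICU exit (the crude percentage with complete follow-up): l / (l + c)
- Cumulative incidence of injury by day t: l / (l + c) × (1 − exp(−(l + c)t))

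The first is the limit of the second as t grows. With complete follow-up, then, the crude percentage is the in-ICU cumulative incidence at end of stay.

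**Step 1: same injury hazard, different exit rates.** With l = 0.06 in every row:

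| c per day | Crude to exit | Cumulative incidence, day 14 | Cumulative incidence, day 28 |
|---|---|---|---|
| 0.10 | 0.06/0.16 = 37.5% | 33.5% | 37.1% |
| 0.15 | 0.06/0.21 = 28.6% | 27.1% | 28.5% |
| 0.20 | 0.06/0.26 = 23.1% | 22.5% | 23.1% |

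Moving from 0.15 to 0.20 gives a risk ratio of 0.21/0.26 = 0.81 with no effect on the injury hazard. In groups of 49 that is about 14.0 against 11.3 injuries. Cumulative incidence shows almost the same shift, so it does not remove the problem by itself.

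**Step 2: how often the tests reject.** 10,000 simulated trials with 49 per group were run for each row at a 5% level. The log-rank test compares the two study groups and censors at death and discharge.

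| l, control v bundle | c, control v bundle | Crude % | Pearson | Yates | Log-rank |
|---|---|---|---|---|---|
| 0.05 v 0.05 | 0.10 v 0.10 | 33.3 v 33.3 | 4.6% | 2.8% | 5.1% |
| 0.05 v 0.05 | 0.10 v 0.15 | 33.3 v 25.0 | 14.8% | 10.6% | 5.2% |
| 0.05 v 0.05 | 0.10 v 0.20 | 33.3 v 20.0 | 32.9% | 25.7% | 5.5% |
| 0.05 v 0.025 | 0.10 v 0.10 | 33.3 v 20.0 | 32.5% | 25.2% | 41.2% |
| 0.05 v 0.025 | 0.10 v 0.05 | 33.3 v 33.3 | 4.9% | 3.1% | 47.3% |

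The third and fourth rows have the same crude percentages: 0.05/0.25 = 20.0% and 0.025/0.125 = 20.0%. One has no effect on the injury hazard and the other halves it, and the crude table cannot tell them apart. In the last row the hazard is halved, but slower exit hides it completely from the table.

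**The case against.** Four counter-arguments deserve weight.

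1. *The crude percentage answers a proper question.* This stands. With everyone followed to exit, it is the risk of injury during the stay. If the bundle itself shortened stays, the resulting fall would be part of its total effect. A reader might infer that the crude percentages misstate injury risk because deaths and discharges are not handled as competing events. The formulas show otherwise. The weakness is in attributing the difference to prevention when the groups are not concurrent.

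2. *The plan already has log-rank and Cox.* In name only. The log-rank test is by VOD status and the Cox model is for risk factors, so neither is stated to compare bundle with control. Nor should one infer that the plan censors deaths and discharges wrongly. Its censoring rule is simply absent, and a log-rank or Cox analysis that censors at exit is a valid comparison of cause-specific hazards.

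3. *Censored survival curves would overstate risk.* They would if one minus Kaplan-Meier were reported as injury risk. With l = 0.05 and c = 0.10 it gives 75.3% at day 28, against a cumulative incidence of 32.8%. The documents plan no Kaplan-Meier curve and no risk read from one, so this cannot be held against them.

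4. *Exit rates may not differ.* They may not, and the documents give no evidence either way. The analysis as written would not reveal it if they did.

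**Conclusion.** The point holds in a limited form. The stated analysis compares a proportion that depends on exit rates as well as on injury rates, in groups drawn from different periods, and no usable time-to-injury comparison of the groups stands beside it. Under the assumed hazards, a difference in exit rates alone can give 28.6% v 23.1%. With a doubled exit rate it makes the Pearson test significant in about a third of trials with no effect on the injury hazard. It can equally conceal a halved hazard.

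These figures show the mechanism and do not estimate what happened in this trial. They assume constant hazards, similar patients within each group, and complete follow-up to exit. The log-rank test keeps its 5% level under those assumptions. It would not protect against a change in patients' underlying injury risk between periods, which is a limit of the sequential design that no choice among these analyses removes. The size and direction of any bias cannot be known from the documents.

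**What to change.** Replace the VOD sentence with text to this effect:

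> Time from ICU admission to first pressure injury will be compared between bundle and control by the log-rank test and by cause-specific Cox regression with study group as a term, censoring at death, discharge and administrative cut-off. Cause-specific hazard ratios for death and for injury-free discharge will be reported beside it, each with a 95% confidence interval. The cumulative incidence of injury by group (Aalen-Johansen) will be given with the risk difference and 95% confidence interval at a day fixed in advance.

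Three further changes belong with it:

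- State whether patients still in the unit when the target is reached are followed to exit or cut off, and report how many are cut off.
- Add date of injury and exit type (death or discharge) to the Patient Information Form.
- Do not rest the conclusion on cumulative incidence or Gray's test alone, since both move with exit rates. Read together, the three hazard ratios show whether a lower injured percentage comes from fewer injuries or from faster exit.

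The cost is two chart fields per patient, a short paragraph of analysis text, and software other than SPSS 23 for the cumulative incidence. The log-rank and Cox methods are already named in the plan.

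### Does listing the target sample size among the end criteria cut off patients still in the ICU, or let newly trained nurses care for remaining controls?

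*Combined protocol and SAP*

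**What the plan says.** Under Inclusion and Exclusion Criteria the plan introduces a list with "The end criteria for the study was determined as follows". It has four items: death, "reaching the desired number of patients, discharging the patient from the clinic", and pressure injury. Three describe what happens to a patient and one describes the study. No separate follow-up rule is given.

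Study Universe and Sample gives the target as "98 patients were included in the study with a minimum number of 49 patients in each group", drawn from patients "who were hospitalized in the intensive care unit between July-December 2021".

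Under Data Collection, Stage 1, controls come first, under routine care. Then: "After completing the patient acquisition of the control group, an appropriate training schedule has been created". Training follows: "The training program has been carried out to 40 nurses working in ICU between 30-45 minutes in 4 separate meetings". Stage 2 applies the bundle to eligible patients up to the target number. Stage 3 then examines injuries in the bundle group. The section opens with "The stages of the study are presented in" and points to Figure 1, which is not reproduced in the text I worked from.

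The Patient Information Form records "date of hospitalization, hospitalization diagnosis, duration of stay in intensive care unit", together with the development and stage of any pressure injury.

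**The concern.** The groups are recruited one after the other in the same unit, so the plan should make clear what happens to patients still admitted at each changeover. Two things could go wrong.

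- **Truncation.** If meeting the target ends observation, patients then in the ICU are counted as injury-free before their risk has run its course. The tests named for categorical comparisons (Yates-corrected, Fisher, Pearson) cannot censor. Cox regression and the log-rank test can, but neither is stated as the bundle-versus-control comparison.
- **Contamination.** If training begins while controls are still admitted, nurses who know the bundle care for them, and their care is no longer purely routine.

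Truncating both groups, or contaminating controls, shrinks the observed difference. Truncating only the bundle group would inflate it, and would show a benefit even if the bundle did nothing. An unstated rule that can move the result either way deserves a check.

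**Working it through.** **Step 1: the text.** A count of patients is reached by the study, not by a patient, and the list is headed as end criteria for the study. Stage 2 uses the same count to say how long eligible patients went on being taken into the bundle group. Stage 3 examines injuries after that. Together these fit a target that closes enrolment. Nothing says an enrolled patient was dropped when it was met. On training, a timetable fitted to nurses' rosters and four meetings come after control enrolment, so some gap is implied.

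**Step 2: inputs.** From the plan: 49 per group, two groups in sequence, July to December (184 days). Assumed, because the plan gives none of them: even accrual over *T* = 91 days per group; exponential stay with mean *L* = 7, 10, 14 or 20 days; injury hazard *h* = 0.03 per day in controls and 0.015 with the bundle; trained nurses give remaining controls the bundle hazard. The plan has no figure of its own on this point to reproduce.

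**Step 3: formulas.**

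- Injury risk under full follow-up: *p* = *h* / (*h* + 1/*L*). For controls at *L* = 7: 0.03 / (0.03 + 0.1429) = 0.174.
- Standard error of the difference: √[(*p*c(1 − *p*c) + *p*b(1 − *p*b)) / 49].
- Patients under observation at last enrolment: *N* = (49/*T*) / (*h* + 1/*L*) + 1, the 1 being the last patient enrolled. For controls at *L* = 7: 0.538 / 0.1729 + 1 = 4.1.
- Risk lost if a group is truncated: *N* × *p* / 49, since with constant hazards each remaining patient still carries risk *p*.
- Drop from contamination after a gap of *g* days: *N*c × exp[−(*h*c + 1/*L*)*g*] × (*p*c − *p*b) / 49.

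**Step 4: results** (risks, differences and drops in percentage points).

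| Mean stay (days) | 7 | 10 | 14 | 20 |
|---|---|---|---|---|
| Control risk | 17.4 | 23.1 | 29.6 | 37.5 |
| Bundle risk | 9.5 | 13.0 | 17.4 | 23.1 |
| True difference | 7.9 | 10.0 | 12.2 | 14.4 |
| Standard error | 6.8 | 7.7 | 8.5 | 9.2 |
| Controls still observed | 4.1 | 5.1 | 6.3 | 7.7 |
| Bundle patients still observed | 4.4 | 5.7 | 7.2 | 9.3 |
| Drop, both groups truncated | 0.6 | 0.9 | 1.2 | 1.5 |
| Drop, contamination, 7-day gap | 0.2 | 0.4 | 0.8 | 1.3 |
| Drop, contamination, 14-day gap | 0.1 | 0.2 | 0.4 | 0.7 |

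Example, truncation at *L* = 20: controls lose 7.73 × 0.375 / 49 = 5.9 points and the bundle group 9.28 × 0.231 / 49 = 4.4, so the difference falls by 1.5. A simulation with 20,000 runs per row agrees to within 0.1 point (1.6 and 0.8 where the last column shows 1.5 and 0.7). The largest ratio is 1.6 / 9.2, about 17% of a standard error. A control cannot be both truncated and later contaminated, so these drops do not add.

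**Step 5: does the window matter?** Two accruals of 91 days use 182 of the 184 days, so a 7-day gap (189 days) overruns. With *T* = 80, two accruals and a 14-day gap take 174 days and fit. The drops become 0.7 to 1.7 points (truncation), 0.2 to 1.5 (7-day gap) and 0.1 to 0.8 (14-day gap). The largest is 1.7 / 9.2, about 19% of a standard error, so the picture is unchanged.

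**The case for a change.** The strongest case for a change is that the direction of bias hangs on a rule nobody wrote down, while one sentence would supply it. If the target means the study-wide 98 and meeting it ends observation, only bundle patients are cut short. Under the same assumptions the difference is then inflated by 0.9 to 4.4 points, up to about half a standard error, and a benefit of about 1.4 to 6.0 points appears when there is none. If training began the day the last control was enrolled, contamination would cost 0.7 to 2.3 points.

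The gap in the text stands. The extremes do not carry the argument. Bundle-only truncation needs three things at once: a study-wide target, though the plan states a minimum for each group; a target that stops observation of patients already enrolled; and a Stage 3 that is analysis only. Zero-gap contamination conflicts with a timetable and four meetings that come after control enrolment.

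The fuller remedies also cost more than a sentence. Under the same assumptions, holding training until the last control leaves means a mean wait of 12 to 33 days. Fitting that into 184 days needs accrual 6% to 22% faster, to recover 0.1 to 1.3 points. Whether the group comparison should be time-to-event, with death and discharge as competing events, is a fair question. It is a separate one and does not turn on this list.

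**Conclusion.** The concern does not call for a change. The plan leaves unsaid whether the target only closes enrolment and whether the last control had left before training began. The sensible reading answers the first, and Figure 1 may answer both. No truncation or contamination is shown to have occurred.

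If either did occur in its ordinary form, the risk difference would fall by about 0.1 to 1.6 points, against a standard error of 6.8 to 9.2. That works against the bundle, so it would not manufacture a positive finding. These figures rest wholly on the assumed hazard, hazard ratio, stay and accrual pace, none of which is in the plan. They show scale only. An analyst who follows each enrolled patient to injury, discharge or death reaches a sound conclusion from the plan as written.

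### Does listing Yates, Fisher and Pearson without a selection rule leave the pressure injury comparison unsound?

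*Combined protocol and SAP*

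**What the plan says.** Under Hypothesis, H1 states that the bundle "is active in preventing pressure injury development". Study Universe and Sample ties the sample size to this outcome: "In order to determine the development status of pressure injuries in the intervention and control groups", at least 49 patients were taken in each group, 98 in all. Stage 3 of Data Collection treats the outcome as present or absent: "it was examined whether any pressure injuries developed in the patients".

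Data Evaluation and Statistical Methods covers all categorical group comparisons in one sentence, which opens "In the categorical comparison of the groups, Yates Correction" and adds Fisher's exact test and Pearson's chi-square. The significance level is .05 and the software is SPSS V23. No expected-count threshold, sidedness or designated test for pressure injury is given. Cox regression is attached to risk factors and the log-rank test to VOD status, so neither is assigned to the comparison of the two groups.

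**The concern.** Three tests that do not always agree are named for the comparison the sample was sized for, with no rule for choosing. If the analyst chose after seeing the table, the verdict on H1 could turn on that choice. Two consequences would follow. Uncorrected Pearson can exceed the 5% level at this sample size. Yates and Fisher sit well below it, which costs power in a study of only 98 patients. Naming one test would take a sentence, so it is natural to ask for it, and to ask for a less conservative exact test at the same time.

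**Working it through.** **Inputs.** From the plan: 49 per group and level .05. Assumed, because the plan is silent: two-sided tests, exactly 49 v 49, a complete yes/no outcome, and every event rate below. The plan's figure of 49 cannot be reproduced, since it gives no rates, effect size or power. As an illustration only, 40% v 15% or 30% v 8% at 80% two-sided power would fit it.

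**Formulas.** Let a and b be the injuries in the two groups and m = a + b.

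- Pearson: X² = 98(a − b)² / [m(98 − m)]
- Yates: X² = 98(|a − b| − 1)² / [m(98 − m)]
- Smallest expected count: min(m, 98 − m)/2

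**Example, 12 v 4.** Here m = 16 and m(98 − m) = 16 × 82 = 1,312. Pearson is 98 × 64 / 1,312 = 4.78 (p = .029). Yates is 98 × 49 / 1,312 = 3.66 (p = .056). Fisher gives p = .053. The smallest expected count is 8.

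**All tables.** There are 50 × 50 = 2,500 results. Pearson rejects in 1,756; Yates and Fisher each reject in 1,660, and in the same tables. The difference is 1,756 − 1,660 = 96 tables, 48 per direction. In 80 of these every expected count is at least 5. Pearson rejects in every table where the others do.

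**Type I error (%), by common risk:**

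| Test | 5% | 10% | 20% | 30% | 50% | Maximum |
|---|---|---|---|---|---|---|
| Yates/Fisher | 0.7 | 1.7 | 2.8 | 3.0 | 3.3 | 3.34 |
| Fisher if an expected count is below 5, else Pearson | 0.8 | 3.9 | 5.2 | 4.9 | 5.4 | 5.44 |
| Pearson | 5.3 | 5.9 | 5.2 | 4.9 | 5.4 | 6.12 |

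**What an analyst would plausibly do** (each reading is an assumption):

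1. Tiers at expected counts of 5 and 25 (Fisher, then Yates, then Pearson). The smallest expected count is at most 49/2 = 24.5, so Pearson is never reached. The decision equals Fisher's in all 2,500 tables, with a maximum of 3.34%.
2. Pearson kept for tables larger than 2×2, such as diagnosis, injury stage or Braden class. The outcome then falls to Yates or Fisher, which agree in every table.
3. Fisher if an expected count is below 5, else Pearson. Maximum 5.44%.
4. Worst case, smallest p-value. Because the rejection regions are nested, this is simply Pearson, with a maximum of 6.12%.

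**Power (%) under assumed risks:**

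| Risks | Yates/Fisher | Boschloo | Fisher-or-Pearson |
|---|---|---|---|
| 40 v 15 | 74.5 | 78.2 | 80.9 |
| 30 v 10 | 62.7 | 68.4 | 72.5 |
| 25 v 8 | 52.6 | 59.1 | 65.4 |
| 20 v 5 | 49.5 | 57.1 | 62.9 |
| 50 v 10 | 99.3 | 99.5 | 99.6 |
| 10 v 1 | 25.9 | 40.5 | 26.6 |

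In the first four rows Boschloo gains 3.7, 5.7, 6.5 and 7.6 points over Yates/Fisher, and loses 2.7, 4.1, 6.3 and 5.8 to the Fisher-or-Pearson rule. It has a clear advantage over both only when injuries are rare (10 v 1). Its maximum type I error is 4.94%.

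**Chance that Pearson and Yates/Fisher disagree:** 0.3% at 50 v 10, 6.4% at 40 v 15, 17.1% at 20 v 5 and 31% at 10 v 1. Under the Fisher-or-Pearson rule, disagreement with Fisher at 10 v 1 is only 26.6 − 25.9 = 0.7%.

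**Drift.** If risk fell from 20% to 15% between the two periods with no bundle effect, the chance of p < .05 is 5.8% for Yates/Fisher, 8.0% for Boschloo and 10.4% for Pearson.

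**The case for a change.** The best case for a change is that conventions differ and none is written. Between the 5/25 tiers and the Fisher-or-Pearson rule, 80 tables change verdict. At 20 v 5% the power difference is 62.9 − 49.5 = 13.4 points, so the choice is not cosmetic for moderate effects. The agreement of Yates and Fisher also depends on exactly equal groups. The plan sets 49 as a minimum, and at 49 v 50 the two differ in 52 tables. The one-sentence remedy is cheap.

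These facts stand, and a line naming the test and its sidedness would be tidy. They do not show an unsound analysis. The 96 is a count of tables that are far from equally likely; the chance of disagreement ranges from 0.3% to 31% on rates the plan does not give. Conservatism is a cost in power, not an error. Of the two replacements one might propose, Boschloo lies outside the listed tests and SPSS V23, and the Fisher-or-Pearson rule may be what the plan already intends.

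The choice of 2×2 test also leaves the larger limits where they are. This is a "quasi-experimental study with a control group" in which the bundle phase began only "After completing the patient acquisition of the control group". Observation ends at events that include "discharging the patient from the clinic, the development of pressure injury in the patient", so follow-up is unequal. No test of a 2×2 table deals with period effects or exposure time. The unassigned roles of Cox and log-rank are a separate question.

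**Conclusion.** No change is called for. The plan does omit a selection rule, but it is the kind of omission an analyst fills with an ordinary convention. At 49 v 49, two-sided, those conventions keep the maximum type I error at 3.34% or 5.44%, and the least favourable choice among the listed tests reaches 6.12%. Changing the method would bring no clear gain. Boschloo improves on Yates/Fisher by about 4 to 8 points in four assumed scenarios, falls about 3 to 6 points short of the Fisher-or-Pearson rule in the same four, and is less protective than Yates/Fisher under the assumed drift between periods (8.0% v 5.8%).

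The type I error figures rest on two-sided testing, exactly 49 complete outcomes per group, and groups that are exchangeable apart from the bundle. The power, disagreement and drift figures rest also on assumed event rates.
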